### 3.9 OFF TREATMENT CRITERIA

1. Progression of disease during treatment on study protocol. Decisions will be made at the time of restaging (restaging planned after the second, fourth and sixth cycles and then every third cycle). However, if clinically indicated, a decision may be made following the first cycle, after obtaining the appropriate staging studies.
2. Grade 3/4 toxicity lasting greater than 2 weeks or when therapy is judged detrimental to the patient's health.
3. Grade 4 hypersensitivity reaction to drug administration (anaphylaxis).
4. Patient non-compliance or voluntary withdrawal.
5. Discretion of the Principal Investigator.
6. Unacceptable toxicities that have not resolved at time of "off treatment" or "off study" must be followed until stabilization or resolution.

The reason for treatment removal and the date the patient was removed will be documented in the Case Report Form.

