#### 3.9.1 Post-Treatment Evaluation (Upon Meeting Off Treatment Criteria)

1. History and physical examination (for medical record only)
2. Laboratory studies: CBC with differential and platelet count, and CHEM 20 Panel.
3. Chest X-ray.
4. Appropriate diagnostic imaging.
5. ECOG performance status assessment

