### 3.10 OFF-STUDY CRITERIA

This study does not involve a preset period of monitoring or follow-up after a patient has reached off treatment status. In most cases the Off-treatment and Off-Study dates will be the same. If a patient has a treatment related toxicity, and in the opinion of the PI it is prudent and medically necessary to monitor the patient further, an individual patient may remain on-study, but off-treatment until such time the PI determines it safe to remove them from study.

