As secondary endpoints, progression free survival and duration of response will also be evaluated, using Kaplan-Meier curves. Progression free survival will be measured from the on-study date until the date of progression or last follow-up if the patient has not progressed. Response duration will be determined beginning at the date a PR or CR is first noted and will last until the patient is noted to have progressive disease relative to the response identified.

Women, 18 years of age or older, from all racial and ethnic backgrounds, will be eligible for the study.

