## **7 SAFETY REPORTING REQUIREMENTS/DATA SAFETY MONITORING PLAN**

### **7.1 Definitions**

#### **7.1.1 Adverse Events**

An adverse event is defined as any reaction, side effect, or untoward event that occurs during the course of the clinical trial associated with the use of a drug in humans, whether or not the event is considered related to the treatment or clinically significant. For this study, AEs will include events reported by the patient, as well as clinically significant abnormal findings on physical examination or laboratory evaluation. A new illness, symptom, sign or clinically significant laboratory abnormality or worsening of a pre-existing condition or abnormality is considered an AE. All AEs must be recorded on the AE case report form.

All AEs, including clinically significant abnormal findings on laboratory evaluations, regardless of severity, will be followed until satisfactory resolution. AEs should be reported up to 30 days following the last dose of study drug. AEs that are considered treatment related, expected, continuing, but not resolvable by 30 days after treatment completion (e.g., alopecia) will not be followed after the 30-day period.

An abnormal laboratory value will be considered an AE if the laboratory abnormality is characterized by any of the following:

- Results in discontinuation from the study
- Is associated with clinical signs or symptoms
- Requires treatment or any other therapeutic intervention
- Is associated with death or another serious adverse event, including hospitalization.
- Is judged by the Investigator to be of significant clinical impact
- If any abnormal laboratory result is considered clinically significant, the investigator will provide details about the action taken with respect to the test drug and about the patient's outcome.

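### PFS is censored at an undefined last follow-up date rather than the last tumour assessment, so unscanned time can count as progression-free and may lift the Kaplan-Meier curve

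*Combined protocol and SAP*

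**What the plan says.** Section 5.4.1 makes PFS and response duration secondary endpoints: "progression free survival and duration of response will also be evaluated, using Kaplan-Meier curves". It defines PFS as follows: "Progression free survival will be measured from the on-study date until the date of progression or last follow-up if the patient has not progressed". The last follow-up date is not defined anywhere. Response duration has a start and an event in 5.4.1, but no censoring date.

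Other sections determine when a patient was last scanned and last seen:

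- **On treatment (3.9 item 1):** "restaging planned after the second, fourth and sixth cycles and then every third cycle". After cycle 6, section 3.1 lets cycles lengthen to 4 or 5 weeks.
- **At treatment stop (3.9.1):** the evaluation includes "Appropriate diagnostic imaging".
- **At study termination (Appendix B, column F):** staging imaging is marked.
- **Unresolved toxicity (3.9 item 6):** it "must be followed until stabilization or resolution". No scans are attached.
- **Off treatment but on study (3.10):** the general case is "In most cases the Off-treatment and Off-Study dates will be the same". The exception, for treatment-related toxicity, is that "an individual patient may remain on-study, but off-treatment until such time the PI determines it safe to remove them from study".
- **Adverse events (7.1.1):** "AEs should be reported up to 30 days following the last dose of study drug".
- **Scans after treatment (3.11):** planned for CR and PR patients only, about every 6 weeks and stretching to every 3 to 4 months.

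**The concern.** Under the RECIST rules in 5.2, progression is mainly a finding on measured or imaged lesions, so a patient is known to be progression-free only up to the last assessment. If last follow-up is read as last contact, a stable-disease patient who stops for toxicity stays in the Kaplan-Meier risk set for a period with no planned scan. That time enlarges the denominator but cannot produce an event.

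A patient seen between scans at data cutoff carries unobserved time for the same reason. Three cycles of 4 or 5 weeks give scan intervals of 3 × 4 = 12 to 3 × 5 = 15 weeks, and responders off treatment may go 3 to 4 months.

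The trial has no control arm, so its PFS will be read against outside figures. An upward error would favour the drug.

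**Working it through.** **1. The plan's own figure.** The documents give no PFS target. The figure in 5.4.1 that can be checked is the early-termination probability: 0.95^12 = 0.540, against the stated 0.54. The full two-stage rule (stop at 0/12, active at 4 or more of 37) has type I error 0.093 and power 0.902. Its only inputs are response counts, so the PFS censoring date cannot alter it.

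**2. Mechanism.** Kaplan-Meier is S(t) = Π(1 − d/n) over event times. If m unscanned patients remain in the risk set, a factor becomes 1 − d/(n + m), which is larger whenever d > 0.

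**3. Inputs.**
- Scans at weeks 6, 12, 18, then every 9 weeks (3.9, with 3-week cycles).
- Exponential progression with a median of 2.2 or 3.1 months. Both come from breast cancer trials in 1.2.4 and are illustrative only.
- Assumed: a proportion w of 5%, 15% or 30% withdrawing for toxicity over 6 months (rate −ln(1 − w)/6 per month).
- Assumed: mean contact after stopping of 1 or 3 months, given to every patient who stops without progression.
- A scan at treatment stop, or none.
- 200,000 simulated patients per setting.

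**4. Benchmark.** At 6 months the last scheduled scan is week 18, which is 18/4.345 = 4.14 months. With no withdrawals, Kaplan-Meier should show 2^(−4.14/2.2) = 0.271 or 2^(−4.14/3.1) = 0.396.

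**5. Six-month PFS for w = 5% / 15% / 30%.**

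| Median (months) | Scan at stop | Mean gap (months) | Censored at last assessment | Censored at last follow-up |
|---|---|---|---|---|
| 2.2 | yes | 1 | 0.268 / 0.262 / 0.252 | 0.271 / 0.271 / 0.272 |
| 2.2 | yes | 3 | 0.268 / 0.263 / 0.253 | 0.274 / 0.283 / 0.299 |
| 2.2 | no | 1 | 0.272 / 0.271 / 0.272 | 0.276 / 0.284 / 0.299 |
| 2.2 | no | 3 | 0.270 / 0.272 / 0.270 | 0.279 / 0.298 / 0.327 |
| 3.1 | yes | 1 | 0.392 / 0.387 / 0.375 | 0.395 / 0.397 / 0.396 |
| 3.1 | yes | 3 | 0.395 / 0.385 / 0.375 | 0.401 / 0.405 / 0.419 |
| 3.1 | no | 1 | 0.395 / 0.395 / 0.395 | 0.399 / 0.406 / 0.420 |
| 3.1 | no | 3 | 0.396 / 0.398 / 0.396 | 0.403 / 0.421 / 0.447 |

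The two rules differ by 0.3 to 4.6 points with a scan at stop and by 0.4 to 5.8 points without. Against the benchmark, the largest excess of last-follow-up censoring is 0.299 − 0.271 = 2.8 points with a scan and 0.327 − 0.271 = 5.6 points without.

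**6. Median.** It was the same under both rules in every setting: week 12 (2.76 months) for a true median of 2.2, and week 18 (4.14 months) for 3.1. The curve drops in steps at scans. With a true median of 3.1 it passes from 2^(−2.76/3.1) = 0.54 at week 12 to 0.40 at week 18, so a shift of a few points does not carry the 50% crossing to another scan. Mean PFS restricted to 9 months rose by about 0.01 to 0.4 months.

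**7. Longer gaps.** With a median of 3.1 months, true PFS at week 27 (6.21 months) is 2^(−6.21/3.1) = 24.9%. With a scan at stop and 9%, 18% or 28% stopping without progression, 12 weeks of later contact gives about 27%, 28–29% and 31–33%. Twenty-six weeks gives about 29%, 33% and 38%.

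**8. Data cutoff.** This route was not simulated. If all patients are scanned in the same weeks it adds little, because someone censored between two scan dates leaves the risk set before the next event time. It matters once scan dates are staggered.

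**The case against.** A reader might infer that the plan prescribes censoring at the last toxicity contact and that the curve is therefore biased upward. The documents do not support that. The defect is an undefined term. Section 3.11, the only place that describes follow-up for PFS, describes it as CT scans with examinations, although for responders only. A patient kept on study for toxicity is due imaging when treatment stops and again at study termination, and 3.10 says the two dates usually coincide. This stands, and it confines the problem to a minority. It does not remove it: 3.9 item 6 requires unresolved toxicity to be followed even past off-study, without scans.

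A reader might also infer a large effect from the drug's neuropathy. Section 1.2.4 points the other way. On this 5-day schedule, grade 3/4 sensory neuropathy was 3% in the phase II breast cancer trial. Elsewhere, grade 3/4 neuropathy resolved after a median of 5.4 weeks, and severe neuropathy generally eased within 1 to 2 months. Section 7.1.1 also ends follow-up of some expected, continuing events at 30 days, which must be reconciled with 3.9 item 6. Applying 12- or 26-week gaps to every patient who stops has no source in the documents. If only 30% of them stay in follow-up (an assumption), 12 weeks of contact gives 25.1–25.3% at 9–18% stopping, against a true 24.9%.

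Last-assessment censoring is not error-free either. With a scan at stop it falls up to about 2 points low (0.252 against 0.271; 0.375 against 0.396), and with a 1-month gap last-follow-up censoring is closer. The 30-day adverse event window is therefore no argument for change. The difference is that last-assessment error does not grow with the gap, while last-follow-up error does.

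**Conclusion.** The point holds as a gap in the definition that can bias the PFS curve upward; a bias that is certain to occur is not shown. Any material bias is upward. At about 6 months it runs from roughly 0 to 6 points, near zero for short contact after an off-treatment scan, and larger only if many patients stop without progression and gaps are long. The sizes rest on assumed stop rates and gaps and on progression rates borrowed from breast cancer trials.

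The median usually does not move. PFS is secondary and descriptive, with no test or threshold, and the two-stage response decision is untouched. The change is still worth making, because PFS is a stated objective of an uncontrolled trial and the remedy is one sentence. Section 5.4.1 also does not list death as a PFS event; that is a separate matter, which this change does not repair.

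**What to change.** In 5.4.1, replace the last-follow-up clause of the PFS definition with: *or, for a patient without progression, the date of the last adequate tumour assessment (the on-study date if there was none after baseline)*. Add that response duration is censored at the same last-assessment date.

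The cost is one sentence, with no extra scans and no change to patient care. Assessment dates are already needed for RECIST, but 3.5.2 labels restaging imaging as outside the research record, so confirm that those dates reach the analysis database. The downside is that reported PFS may be slightly shorter.

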#### 5.4.2 Duration of trial:

It is expected that 1 to 4 patients may be accrued onto this study per month. In order to accrue up to 76 patients (the maximum requested) it is anticipated that about 18 to 24 months will be needed. **Furthermore, the trial will be terminated for futility if less than 12 patients are enrolled in the first 9 months of the trial.**

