### Design

- Phase II study, open, non-randomized
- Ixabepilone will be administered at a dose of 6mg/m^2 daily on days 1 through 5, every three weeks.
- Restaging will be done every two cycles using RECIST
- Planned maximum enrollment 76 persons

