#### 5.4.1 Trial Design:

This trial of Ixabepilone in patients with cervical carcinoma will be conducted using a two-stage optimal design (Simon, R, Controlled Clinical Trials, 10:1-10, 1989). With  $\alpha = 0.10$  (the probability of incorrectly accepting a poor agent), and  $\beta = 0.10$  (the probability of incorrectly rejecting a good agent), we will try to rule out an undesirably low overall response (PR+CR) probability of 5% ( $p_0 = 0.05$ ) in favor of a level indicative of modest activity, 20% ( $p_1 = 0.20$ ).

Several histologic subtypes of cervical carcinoma are recognized including: (1) squamous cell (2) adenocarcinoma (3) adenosquamous carcinoma and (4) other. Among these, squamous is the most common histologic diagnosis, with adenocarcinoma second in frequency. While chemotherapy has not been shown to be very effective in cervical carcinoma, differences among the histologic subtypes in response to therapy may exist. In order to properly evaluate the activity of ixabepilone in cervical cancer, we will stratify patients into two cohorts according to histologic subtypes: (1) squamous cell (2) non-squamous including adenocarcinoma, adenosquamous carcinoma and non-squamous-not otherwise specified.

Initially, 12 evaluable patients will be enrolled in each of the two cohorts. If 0/12 demonstrate an objective response (PR +CR), then accrual to that cohort will stop and the agent will be considered inactive in this population. If one or more patients have a response, accrual will continue until a total of 37 evaluable patients have been enrolled in that cohort. If 1 - 3 of 37 patients demonstrates a response in a cohort, this will be

considered insufficient activity, and the agent will not be considered worthy of further development in that cohort. If 4 or more of 37 patients in the entire cohort have a response, then the agent will be considered active in that group (and at least potentially able to produce a response level consistent with 20%). Under the null hypothesis ( $p_0 = 0.05$ ), the probability of early termination of accrual to any one group is 0.54. With two cohorts of patients, the maximum number of evaluable patients in the two cohorts would be 74. However, in the event that an inevaluable patient is enrolled in each cohort, a total enrollment ceiling of 76 patients will be requested. Our goal is to enroll adenocarcinoma patients, but we do not want to refuse squamous cell carcinoma patients who have no other therapeutic options.

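### Does the forecast of about 18 to 24 months for 76 patients need correcting, given an expected accrual of 1 to 4 per month?

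*Combined protocol and SAP*

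**What the plan says.** Section 5.4.2 (Duration of trial) gives the rate first: "It is expected that 1 to 4 patients may be accrued onto this study per month". The next sentence gives the duration: "In order to accrue up to 76 patients (the maximum requested) it is anticipated that about 18 to 24 months will be needed". The section ends with an accrual rule: "the trial will be terminated for futility if less than 12 patients are enrolled in the first 9 months of the trial".

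The figure of 76 is a ceiling. Section 5.4.1 (Trial Design) plans up to 37 evaluable patients in each of two histologic cohorts, so "the maximum number of evaluable patients in the two cohorts would be 74". It allows one inevaluable patient per cohort, hence "a total enrollment ceiling of 76 patients will be requested". The Design part of the Précis agrees: "Planned maximum enrollment 76 persons". A cohort reaches 37 only if at least one of its first 12 evaluable patients responds. Under the 5% null response rate, "the probability of early termination of accrual to any one group is 0.54".

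No section names an average or planning rate within the range of 1 to 4.

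**The concern.** The rate and the duration stand in adjacent sentences, and a reader will divide one into the other. The result does not match the forecast. The full stated range implies a far wider and later window than 18 to 24 months, and the lower end of the forecast cannot quite be reached even at the top rate. The sentence is tied expressly to the maximum of 76, so early closure of a cohort does not explain the difference.

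If the forecast is too short, a scientific or ethics committee would approve the trial on too favourable a view of its feasibility. A two-cohort trial that is slow to fill may also be abandoned before the second stage is complete, leaving the response question unanswered.

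**Working it through.** **Inputs.** Rate 1 to 4 per month, duration about 18 to 24 months, and the floor of 12 patients in 9 months (Section 5.4.2). Ceiling 76 = 2 × 37 + 2, first stage of 12 per cohort, and null and target response rates of 5% and 20% (Section 5.4.1).

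**Can the stated duration be reproduced?** Months needed = 76 / monthly rate.

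| Patients per month | Months to 76 |
|---|---|
| 4 (stated maximum) | 76/4 = 19.0 |
| 3 | 76/3 = 25.3 |
| 2 | 76/2 = 38.0 |
| 1 (stated minimum) | 76/1 = 76.0 |

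The stated range gives 19 to 76 months, so the forecast is not reproduced from the range as a whole.

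**What rate does the forecast imply?** Rate needed = 76 / months.

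- 18 months: 76/18 = 4.22 per month, above the stated maximum. At 4 per month, 18 months yields 4 × 18 = 72 patients, 4 short of 76.
- 24 months: 76/24 = 3.17 per month, inside the stated range and in its upper third.
- Counting only the 74 evaluable patients barely helps: 74/18 = 4.11 and 74/24 = 3.08.

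The 24-month end is optimistic but not contradicted. The 18-month end is out by one month on a figure given as approximate.

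**Is there a single correct duration?** No. The midpoint of the range, 2.5 per month, would give 76/2.5 = 30.4 months, but the plan does not say that accrual averages at the midpoint. Thirty months illustrates the sensitivity; it is not a replacement figure.

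**How many patients would the trial expect to enrol?** Expected evaluable total = 2 × [12 + 25 × (1 − probability of stopping after 12)].

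- Response rate 5% in both cohorts: stopping probability 0.95^12 = 0.540, which reproduces the plan's 0.54. Expected total 2 × (12 + 25 × 0.460) = 47.0. Over 24 to 18 months this needs 47/24 = 1.96 to 47/18 = 2.61 per month.
- Response rate 20% in both: 0.80^12 = 0.069. Expected total 2 × (12 + 25 × 0.931) = 70.6, needing 70.6/24 = 2.94 to 70.6/18 = 3.92 per month.

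For expected rather than maximum enrolment, then, 18 to 24 months fits the stated range at both response rates. The sentence does not say this, so it does not rescue the wording, but it shows the order of magnitude is not unreasonable.

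**Does the duration enter anything else?** The floor of 12 in 9 months is 12/9 = 1.33 per month; it lies inside the stated range and is set independently of the 18 to 24 months. The two-stage rule (0 of 12, then at least 4 of 37) depends on patient counts only. Recomputed exactly, its type I error is 0.093 and its power 0.902, within the planned 0.10 and 0.90. Progression-free survival and response duration are measured from each patient's own dates. None of these uses the forecast.

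**The case for a change.** The strongest case for a change is that the forecast rests on a rate the plan does not disclose, beside a sentence telling readers to expect as few as 1 per month. The low end is not a rate at which the trial would finish: with Poisson accrual (an assumption) at 1 per month, the chance of fewer than 12 patients by month 9 is about 0.80. The 9-month rule is also a weak safeguard against moderately slow accrual, since a trial running just at the floor would need 76/1.33 = 57 months.

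Pooled division may even flatter the forecast. Reaching 76 means filling both cohorts with 38 patients each. Section 1.2.1 puts squamous disease at 75 to 80% of cases. If enrolment followed that mix (an assumption), non-squamous patients would arrive at 0.8 to 1.0 per month even at 4 per month overall, and 38 of them would take 38/1.0 = 38 to 38/0.8 = 47.5 months. Section 5.4.1 does state a goal of enrolling adenocarcinoma patients, which could shift the mix.

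All of this stands as a comment on feasibility: the forecast is at the favourable end and its basis is not shown. What it does not show is any effect on the conduct or interpretation of the trial. Slow accrual would lengthen the calendar or trigger the existing 9-month rule, and both happen in the same way whether Section 5.4.2 prints 18 to 24 months or something longer.

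**Conclusion.** No change is needed. The observation is arithmetically sound but modest. At 1 to 4 per month, 76 patients take 19 to 76 months. The stated 18 to 24 months corresponds to about 4.2 down to 3.2 per month, so the lower end misses the top rate by one month and the upper end is attainable but optimistic. These figures rest only on division of numbers in the plan. Any single alternative duration would need an average rate that the plan does not give.

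The missing planning rate is a small gap in a planning sentence. No analyst needs it and no decision depends on it. The ceiling of 76, the 12-in-9-months rule, the type I error, the power and the response thresholds are unaffected, and the plan followed as written gives the same trial and the same conclusions. If the section is being edited for another reason, stating the assumed average rate would help a reader judge feasibility, but that is optional.

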### 5.5 MULTI-INSTITUTIONAL GUIDELINES

Not applicable

## 6 Human Subjects Protections

### 6.1 RATIONALE FOR SUBJECT SELECTION

#### 6.1.1 Selection based on gender, ethnic background, or race

Subjects from all racial/ethnic groups are eligible for this study if they meet the eligibility criteria. To date, there is no information that suggests that differences in drug metabolism or disease response would be expected in any one patient group. Efforts will be made to extend accrual to a representative population, but in this preliminary study, a balance must be struck between patient safety considerations and limitations on the number of patients exposed to potentially toxic treatments on the one hand and the need to explore ethnic aspects of clinical aspects of clinical research on the other. If differences in the outcome which correlate with ethnic identity are noted, accrual may be expanded or a follow-up study may be written to investigate these differences.

